# **1.0 INTRODUCTION**

This statistical analysis plan (SAP) provides details of the statistical analyses that have been outlined within the protocol for study ACE-CL-001 Protocol Amendment 13 (dated August 25th, 2021), which is entitled "A Phase 1/2, Multicenter, Open-label, and Dose-escalation Study of ACP-196 in Subjects with Chronic Lymphocytic Leukemia, Richter's Syndrome or Prolymphocytic Leukemia". From here on, acalabrutinib will be used in place of ACP-196 in this document.

The scope of the SAP will cover safety and efficacy analyses. Pharmacokinetic (PK) and pharmacodynamic (PD) analyses will be provided in the respective reports. Analysis of electrocardiogram (ECG) data will be performed by an Acerta designated vendor and a separate detailed report will be included to the interim Clinical Study Report (CSR).

If there are differences between protocol specified analyses and the SAP, the SAP will supersede protocol. Major differences will be noted and rationale will be provided in Section 13.0 of this document and the interim CSR.

To support the acalabrutinib New Drug Application (NDA) for relapsed or refractory Mantle Cell Lymphoma (MCL) in 2017, an interim CSR of study ACE-CL-001 was provided consisting of safety analyses for all disease subgroups and efficacy analyses for the relapsed or refractory (RR) disease subgroup as assessed by the investigator. Independent Review Committee (IRC) assessment was not available at this time and was not included in the interim CSR per Protocol Amendment 8 (dated 08 January 2016).

To support the acalabrutinib supplemental New Drug Application (sNDA) for previously untreated and relapsed or refractory chronic lymphocytic leukemia (CLL) in 2019, an interim CSR of study ACE-CL-001 with updated datasets was provided consisting of safety analyses and efficacy analyses for the treatment naïve (previously untreated) and relapsed or refractory (RR) disease subgroup as assessed by the investigator. The requirement of IRC assessment of response was removed in Protocol Amendment 10 (dated 22 February 2018).

### 2.0 STUDY OBJECTIVES

The primary objectives of this study are to:

- Establish the safety and the maximum tolerated dose (MTD) of orally administered acalabrutinib in subjects with chronic lymphocytic leukemia (CLL)/small lymphocytic lymphoma (SLL).
- Determine pharmacokinetics (PK) of orally administered acalabrutinib and identification of its major metabolite
- The secondary objective is to evaluate tumor response by overall response rate (ORR), duration of response (DOR), and progression-free survival (PFS).

[figure not shown]
• CCI

### **3.0 OVERALL STUDY DESIGN**

This study is a Phase 1/2, multicenter (approximately 15 global centers), open-label, nonrandomized, sequential group, dose-escalation study. The phase 1 portion is a dose escalation to establish the maximum tolerated dose (MTD) and the phase 2 expansion portion is to expand sample size on selected dose levels/regimens and additional indications. Table 2 summarizes the revision history of dose regimen and revision history of sample size from protocol original version to amendment 8. For more details on study design, please refer to protocol. Protocol amendments and revision dates are as follows:

[figure not shown]
- Original 01 October 2013
- Amendment 1 18 December 2013
- Amendment 2 06 May 2014
- Amendment 3 03 July 2014
- Amendment 4 22 September 2014
- Amendment 5 14 February 2015
- Amendment 6 01 May 2015
- Amendment 7 14 December 2015
- Amendment 8 08 January 2016
- Amendment 9 30 March 2017
- Amendment 10 22 February 2018
- Amendment 11 17 January 2020
- Amendment 12 18 January 2021
- Amendment 13 25 August 2021

### STUDY SCHEMA FOR DOSE-ESCALATION COHORTS

Note: No DLTs occurred during dose escalation and the MTD was not reached. Under Amendment 4, subjects in Cohort 3 were switched to COL Under Amendment 5, subjects in Cohort 1, Cohort 2a, and Cohort 4a were switched to COL Under Amendment 6, subjects in Cohort 2c and in Cohort 4b COL Abbreviations: bid = twice daily; DLT = dose-limiting toxicity; MTD = maximum tolerated dose; qd = once daily

### STUDY SCHEMA FOR TREATMENT SUBGROUPS (DISEASE SUBGROUP)

Note: Under Amendment 6, subjects in Cohort 7 were switched to CCIAbbreviations: bid = twice daily; qd = once daily

### 4.0 SAMPLE SIZE CONSIDERATION

#### Phase 1 Dose Escalation

The design of the Phase 1 (ie, dose-escalation portion) of the study was not determined based on power considerations. The MTD was defined as the largest daily dose for which < 33% of the subjects experienced a DLT during Cycle 1. No DLT was observed during the dose escalation phase of the study and the MTD was not reached. DLT was reviewed at the time all subjects within each escalation cohort completing one cycle of treatment. The summary of review and findings are filed at Acerta's Trial Master File.

### Phase 2 Expansion

Protocol Original version to Amendment 2: There was no expansion cohort in these protocol versions. Original version included dose escalation cohorts 1, 2a, 2b escalation, and 3. Amendment 2 added dose escalation cohorts 4a and 4b. All cohorts were relapse or refractory (RR) subjects.

Protocol amendment 3: Expansion cohort 7: treatment naive (TN), 8a: ibrutinib intolerant (II), 9 Richter's Syndrome or Prolymphocytic Leukemia (RS/PLL) with 8 to 12 subjects each, and cohort 10 (ibrutinib RR) with 12 to 16 subjects were added.

Protocol amendment 4: Existing subjects in cohort 8a (II) were switched from dose level and new subjects enrolled to this cohort received **CCI** (cohort 8b) starting from Cycle 1 Day1. Expansion cohorts 2b expansion, 2c (RR), 8b (II), and 11 (TN) were added. The sample size for all expansion cohorts were changed to 30 subjects each based on Simon's 2-stage design.

Each cohort of the Phase 2 expansion portion will test the null hypothesis that the ORR is  $\leq$  10% against the alternative hypothesis that it is  $\geq$  35%. Using Simon's optimal 2-stage design (Simon 1989), a total sample size of 30 subjects per cohort has power = 0.90 to achieve a 1-sided significance level of  $\leq$  0.025. In Stage 1, 11 subjects will be enrolled per cohort; if  $\geq$  2 subjects (18%) achieves an objective response of a partial remission (PR)/PR with lymphocytosis (PRL) or better within the first 4 cycles of treatment, then that cohort will continue to full enrollment. Under the Simon 2-stage design, an ORR of  $\geq$  23% (ie,  $\geq$  7 subjects responding of 30 subjects evaluated) will achieve a significance level of  $\leq$  0.025. Using an exact binomial confidence interval (CI), an ORR of 23% (ie, 7 subjects responding of 30 subjects of 30 subjects, Table 1 shows the 2-sided exact 90% binomial CIs on the true response rate for the range of possible values for the observed response rate.

		90%CI	
Responses, n	Response Rate, %	Lower Bound	Upper Bound
0	0%	0.0%	9.5%
1	3.3%	0.2%	14.8%
2	6.7%	1.2%	19.6%
3	10.0%	2.8%	23.9%
4	13.3%	4.7%	27.9%
5	16.7%	6.8%	31.9%
6	20.0%	9.1%	35.7%
7	23.3%	11.5%	39.4%
8	26.7%	14.0%	43.0%

Abbreviation: CI = confidence interval, ORR = overall response rate

Protocol amendment 5: The sample size was increased from 30 subjects to 200 subjects for cohort 2b (RR) and to 60 subjects for cohort 11 (TN) to provide safety and efficacy data in support of the Phase 3 program of acalabrutinib in CLL.

Protocol amendment 6: No change on sample size.

Protocol amendment 7: The sample size was decreased from 200 subjects to 65 subjects for cohort 2b (RR) which is considered sufficient to meet the primary objective of this study. The sample size for cohort 8b (II) was increased from 30 subjects to 35 subjects to obtain additional safety and efficacy data in ibrutinib intolerant population.

Protocol amendment 8-13: No change on sample size.

A total of approximately 286 eligible subjects were planned to be enrolled in this study.

Cohort	Dose Regimen	Treatment Phase	Disease Subgroup	Planned Sample Size*	Protocol Version the Cohort First Added	Revision History of Dose Regimen	Revision History of Sample Size
1	CCI	Escalation	RR	6	Original	CCI	
2a		Escalation	RR	6	Original		
3		Escalation	RR	6	Original		
4a		Escalation	RR	6	A2		
2b		Escalation / Expansion	RR	65	A2/A4		A2 (N=6) dose escalation $\rightarrow$ A4 (N=30) expansion $\rightarrow$ A5 (N=200) $\rightarrow$ A7 (N=65)
4b		Escalation	RR	6	A2		
2c		Expansion	RR	30	A4		
7		Expansion	TN	30	A3		$A3 (N=8-12) \rightarrow A4 (N=30)$
11		Expansion	TN	60	A4		$A4 (N=30) \rightarrow A5 (N=60)$
8a		Expansion	Ibr. Intol.	8-12	A3		A3 (N=8-12) $\rightarrow$ A4 subjects switched to 100 mg bid
8b		Expansion	Ibr. Intol.	35	A4		$A 4 (N=30) \rightarrow A7 (N=35)$
9		Expansion	RS/PLL	30	A3		$A3 (N=12) \rightarrow A4 (N=30)$
10		Expansion	Ibr. RR	6	A3		A3 (N=16) $\rightarrow$ A4 (N=30) $\rightarrow$ A7 (N=6)

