### 6.0 STATISTICAL METHODS

### 6.1 Data Presentation

Tables and figures will be summarized by disease subgroup and cohort unless otherwise specified.

No formal tests of hypotheses will be performed. P-values, if presented, will be provided for descriptive purpose. Descriptive statistics (number of subjects, mean, and standard deviation, median, minimum, and maximum) will be presented for continuous variables including baseline demographic, disease characteristics, study drug administration, efficacy and safety outcomes. Categorical variables will be summarized as the number and percentage of subjects per category. Confidence intervals [CIs] may be included as appropriate.

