### 11.1 Overall Response Rate (ORR)

ORR is the proportion of subjects who achieve complete remission (CR), CR with incomplete marrow recovery (CRi), or partial remission (PR) while on treatment before the initiation of new anti-cancer therapy or stem cell transplant. The corresponding 95% CIs using exact binomial distribution will be provided.

ORR will be summarized using Efficacy Evaluable Population and All Treated Population. Efficacy Evaluable Population is the primary analysis population.

For CLL disease subgroups (ie, except RS/PLL disease subgroup), ORR including PRL as a response will also be summarized in the same fashion.

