### **13.0 DEVIATIONS FROM PROTOCOL AND OTHER ISSUES**

Time to initial response is not specified as an efficacy endpoint in the protocol. Since it provides information about the onset of response, it is added to the SAP as an efficacy endpoint.

If there are changes to the planned analyses described in the SAP, they will be described in the clinical study report.

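### Does the Simon two-stage test in Section 4.0 contradict the statement in Section 6.1 that nothing is formally tested?

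*SAP*

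**What the plan says.** SAP Section 4.0 goes through the protocol versions in turn and records how the expansion cohorts were sized under each. The Amendment 4 entry sets every expansion cohort to 30 on Simon's optimal two-stage design. It states: "Each cohort of the Phase 2 expansion portion will test the null hypothesis that the ORR is" 10% or lower, "against the alternative hypothesis that it is" 35% or higher, with power 0.90 at a one-sided level of 0.025. Stage 1 takes 11 subjects and the cohort continues if at least 2 respond. At least 7 responders out of 30 meets the significance level.

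Later entries resize some cohorts. Amendment 5 changes 2b and 11. Amendment 7 changes 2b again, and "The sample size for cohort 8b (II) was increased from 30 subjects to 35 subjects". The last entry reads "Protocol amendment 8-13: No change on sample size". Table 2 still shows Cohorts 2c, 7 and 9 at 30.

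Section 6.1, under Statistical Methods, says "No formal tests of hypotheses will be performed" and makes any p-value descriptive. Section 11.1 says of ORR: "The corresponding 95% CIs using exact binomial distribution will be provided". Section 1.0 says of departures from the protocol's analyses: "Major differences will be noted and rationale will be provided in Section 13.0 of this document and the interim CSR". Section 13.0 records one: "Time to initial response is not specified as an efficacy endpoint in the protocol".

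**The concern.** One section announces a hypothesis test in the future tense and another says there are none. For the resized cohorts the Amendment 4 text is plainly out of date. For Cohorts 2c, 7 and 9 it is less plain: no later entry touches their size, so the Simon design is still the only stated basis for their 30 subjects, and nothing labels its decision rule as sizing-only or withdrawn. Section 13.0 is silent on it.

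What would be at stake is the wording of a claim on a secondary objective. With 7 responders out of 30, a report could lean on Section 4.0 and call the result significant, while Section 6.1 makes it descriptive and the planned 95% interval still includes 10%.

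**Working it through.** **Inputs.** From Section 4.0: null rate 0.10, alternative 0.35, Stage 1 size 11 (continue if at least 2 respond), total 30, success if at least 7 respond, one-sided level 0.025, power 0.90. From Section 11.1: exact two-sided 95% interval. From Table 2: planned cohort sizes.

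**1. The plan's own design.** The probability of declaring success is

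P(success | p) = Σ over x = 2 to 11 of P(X₁ = x | 11, p) × P(X₂ ≥ 7 − x | 19, p).

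- p = 0.10: 0.0220, within 0.025.
- p = 0.35: 0.9004, matching the stated power of 0.90.

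A search over two-stage designs meeting both constraints returns the same optimal design. The Section 4.0 figures are sound.

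**2. Where the two readings differ.** The Clopper-Pearson 95% limits for x of n are Beta(0.025; x, n − x + 1) and Beta(0.975; x + 1, n − x).

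| Responders | 95% interval | Excludes 10%? | Section 4.0 rule |
|---|---|---|---|
| 7/30 | 9.9% to 42.3% | No | Met |
| 8/30 | 12.3% to 45.9% | Yes | Met |

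The gap at 7/30 arises because the two-stage rule gains from the chance of stopping at Stage 1 (0.697 when p = 0.10). The single-stage tail P(X ≥ 7 | 30, 0.10) is 0.0258, just above 0.025. From 8 responders upward the two readings agree on whether 10% is excluded.

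**3. How often that happens.** The probability of continuing past Stage 1 and ending on exactly 7 of 30 is Σ over x = 2 to 7 of P(X₁ = x | 11, p) × P(X₂ = 7 − x | 19, p):

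| True ORR | 10% | 25% | 30% | 35% | 50% |
|---|---|---|---|---|---|
| Probability | 1.5% | 13.8% | 10.1% | 5.4% | 0.16% |

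It also needs a denominator of exactly 30. The primary ORR population is the Efficacy Evaluable Population (Sections 5.3 and 11.1), which may be smaller than the planned number.

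**4. Cohorts concerned.** 2c, 7 and 9: 30 + 30 + 30 = 90. Total: 5 × 6 + 65 + 30 + 30 + 60 + 35 + 30 + 6 = 286, with 8a counted inside 8b. The 90 are the subjects in the named cohorts, not subjects whose analysis would change.

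**5. What an analyst would do.**

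| Section | Function | Test of ORR against 10%? |
|---|---|---|
| 4.0, Amendment 4 entry | How N = 30 was chosen | Stated, as sizing rationale |
| 6.1 | Rules for all analyses | Excluded |
| 11.1 | ORR analysis | None; exact 95% interval |

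The two sections that instruct the analyst agree. Following them gives one result, a proportion with its exact 95% interval, in every cohort.

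**The case for a change.** The best case for a change is that Section 4.0 is the SAP's sample size section and not merely a log. For 2c, 7 and 9 nothing supersedes the Amendment 4 entry, so its decision rule is arguably still live, and the clash with Section 6.1 lies wholly inside the SAP. RR and TN efficacy has already been reported in interim study reports (Section 1.0), so the status of a result should not be left to choice. A sentence would cost almost nothing.

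Part of this stands: the future tense is untidy, and no sentence marks the Simon text as sizing-only. But a current sample size does not make the test current. A design can fix a cohort's size and govern its Stage 1 enrolment while the final ORR is reported descriptively. Nor is the choice open: to claim a met significance level, a report would have to disregard an explicit sentence in Section 6.1.

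Three related points add nothing.

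- **Section 13.0.** It records departures from the protocol's analyses. The protocol is not at hand, so its silence on the Simon test shows no omission.
- **Resized cohorts.** Applying the 7-responder cut-off to 35, 60 or 65 subjects would inflate alpha, but Section 4.0 ties that cut-off to 30 subjects evaluated and gives separate reasons for resizing 2b, 11 and 8b.
- **Cohort 10.** Its cut to 6 is missing from the Amendment 7 text but shown in Table 2. That is editorial.

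**Conclusion.** No change is needed. The clash is one of tense and labelling between a dated sizing rationale and the operative analysis rules, and the operative rules are clear and consistent with each other. The design arithmetic is correct (alpha 0.0220, power 0.9004). The only numerical disagreement is at exactly 7 of 30, and there the plan already settles what is reported: a descriptive estimate with a 95% interval of 9.9% to 42.3%. A clarifying sentence would do no harm, but it would relabel history without altering any sample size, error rate, estimate, analysis or permitted conclusion.

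This rests on two assumptions: that the Amendment 4 entry is read as part of the version-by-version history in which it stands, and that Section 6.1 governs all efficacy analyses, as its place under Statistical Methods indicates. If the current protocol does still specify the test as an analysis, Section 1.0 already says where a major difference is to be recorded.

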#### Table 2. Summary of Dose Regimen and Sample Size

\* Planned sample size was based on the sample size in Amendment 8 except Cohort 8a, which was lumped with Cohort 8b into one cohort and subsequently renamed "Cohort 8 Ibrutinib Intolerant CCI" in Amendment 4. RR = relapse or refractory, TN = treatment naïve, Ibr. Intol. = ibrutinib intolerant, RS = Richter's syndrome, PLL= prolymphocytic leukemia, Ibr. = ibrutinib

bid = twice daily, qd = once daily

### **5.0 ANALYSIS POPULATIONS**

Analysis populations will be defined in the following sections. In each analysis population, subjects will be analyzed at the dose level they were assigned to at the time of enrollment. The safety analyses will be performed on the All Treated Population. Primary efficacy analyses for ORR and DOR will be based on the Efficacy Evaluable Population. PFS and time to initial response analysis will be based on the All Treated Population. Response will be assessed by investigators. Response assessed by IRC is not available for the interim CSR but will be analyzed and included in the final CSR.

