### **11.0 EFFICACY ANALYSIS**

Response will be assessed by investigators based on Hallek 2008 with incorporation of the clarification for treatment-related lymphocytosis per Cheson 2012 for CLL/SLL and Cheson 2014 for Richter's Syndrome.

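### Does the promise of an IRC-assessed response analysis in SAP Section 5.0 need correcting, given that the IRC requirement was removed in Amendment 10?

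*SAP*

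**What the plan says.** Section 5.0 (Analysis Populations) first names the assessor: "Response will be assessed by investigators". The next sentence concerns the Independent Review Committee (IRC): "Response assessed by IRC is not available for the interim CSR but will be analyzed and included in the final CSR".

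Section 1.0 (Introduction) gives the history. For the 2017 interim report, prepared under Amendment 8, IRC assessment was not yet available and was left out. For the 2019 interim report, efficacy was investigator-assessed, and the section adds: "The requirement of IRC assessment of response was removed in Protocol Amendment 10 (dated 22 February 2018". It also says that this SAP "provides details of the statistical analyses that have been outlined within the protocol for study ACE-CL-001 Protocol Amendment 13", which Section 3.0 lists as "Amendment 13 25 August 2021", and that the SAP prevails where it differs from the protocol.

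Section 11.0 (Efficacy Analysis) opens with "Response will be assessed by investigators based on" and cites the response criteria. Sections 11.1 to 11.4 define overall response rate (ORR), progression-free survival (PFS), duration of response (DOR) and time to initial response without mentioning the IRC.

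Section 13.0 lists one difference from the protocol, the addition of time to initial response, and closes with "If there are changes to the planned analyses described in the SAP, they will be described in the clinical study report".

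**The concern.** Read together, the sections seem to pull apart. Section 5.0 commits the final report to an IRC analysis without condition. Section 1.0 says the protocol stopped requiring IRC assessment three amendments before the version this SAP serves. Section 11, where an analyst would look for the method, is silent on the IRC. The similar statement about the 2017 report in Section 1.0 suggests that the Section 5.0 sentence was carried forward and never updated.

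The study is open-label and tumor response is its secondary objective, so whether response is read independently matters to anyone judging the efficacy results. If the promise is stale, the plan announces an analysis that nobody intends to run. If it is live, the plan announces an analysis that Section 11 does not describe. The worry is that the choice between reporting and not reporting independent reads would be made only when the final report is written.

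**Working it through.** No figure in the plan depends on this point, so the check sets the statements side by side.

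**1. Timing.** Amendment 10 is dated 22 February 2018 and Amendment 13 is dated 25 August 2021.
- 22 February 2018 to 22 February 2021: 365 + 365 + 366 = 1096 days.
- 22 February 2021 to 25 August 2021: 184 days.
- Total: 1096 + 184 = 1280 days, and 1280 / 30.4375 = 42.1 months.
- Amendments 11, 12 and 13 lie in between or at the end, so three.

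This confirms that the removal came well before the protocol version in force. It measures elapsed time and says nothing about the size of any effect on a result.

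**2. Do Sections 1.0 and 5.0 contradict each other?** Section 1.0 says a requirement was removed. It does not say that reads were stopped, discarded or barred from analysis. Section 5.0 says an analysis will be done. An analysis that is no longer required can still be planned, so both statements can be true. Where protocol and SAP do differ, Section 1.0 lets the SAP govern, which leaves the Section 5.0 sentence standing.

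**3. Do Sections 5.0 and 11 contradict each other?** Section 5.0 itself places investigator assessment and later IRC reporting in adjacent sentences: investigators for the analyses described, the IRC added in the final report. Section 1.0 frames this SAP largely around an interim report, for which Section 5.0 says IRC response is unavailable. Investigator-only wording in Section 11.0 fits that scope.

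**4. Could an analyst carry out the IRC analysis from what is written?** Largely, yes. The response categories and the exact 95% interval in Section 11.1, the event and censoring rules in Section 11.2 and the start and end points of DOR in Section 11.3 do not depend on who reads the scans. One choice is open: whether the Efficacy Evaluable Population in Section 5.3, which needs at least one response assessment after first dose, would count IRC or investigator assessments. Section 11.1 already limits the consequence, because "ORR will be summarized using Efficacy Evaluable Population and All Treated Population", and the All Treated denominator is the same for either assessor.

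**5. What happens under each reading?**

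| | IRC reads exist and are analyzed | IRC reads do not exist or are not analyzed |
|---|---|---|
| Investigator ORR, DOR, PFS | unchanged | unchanged |
| Formal tests | none planned (Section 6.1) | none planned (Section 6.1) |
| What the final report shows | an additional set of response results | a stated departure from the SAP (Section 13.0) |

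The investigator-assessed results are the same in both columns.

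**The case for a change.** The strongest case for a change runs as follows. A SAP should not promise an analysis whose protocol basis it reports as withdrawn without saying whether the promise survives. Section 1.0 also asks for major differences from the protocol to be listed with a rationale in Section 13.0, and that section does not mention the IRC. So either the analysis was kept on purpose and is undeclared, or it was not kept and the Section 5.0 sentence is wrong. Both call for an edit, which would cost one or two sentences.

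Part of this stands. The sections sit awkwardly together, and the sentence may well be a remnant, although the document does not say so. The rest is weaker:

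- The silence of Section 13.0 is inconclusive. Only major differences must be listed, and whether an IRC analysis differs from Amendment 13 at all cannot be judged without that protocol.
- It is too strong to say that a reader cannot tell what the final report will contain. Section 5.0 says so directly. The doubt arises only after one supposes that the sentence is obsolete.
- The fear of a late, results-driven choice points the other way. As written, the SAP holds the sponsor to reporting IRC response if it can, and leaving it out would be a visible departure to be described in the report. Deleting the clause would remove the SAP's only commitment to independent review in an open-label study.

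**Conclusion.** The observation is accurate, but it does not call for a change to the plan. There is a drafting tension between Sections 1.0, 5.0 and 11 and no logical contradiction. Following the SAP as written gives sound results: response is analyzed by investigator assessment as specified, IRC response is added to the final report if it is available, and otherwise the report records its absence. The effect on any investigator-assessed estimate is nil, and no error rate or decision rule is touched. No effect on an IRC-based estimate can be worked out, because the SAP does not say whether such reads exist or for how many subjects.

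This rests on two assumptions. One is that the precedence rule in Section 1.0 and the reporting rule in Section 13.0 are followed. The other is that Amendment 13, which is not at hand, does not prohibit an IRC analysis; nothing in the SAP suggests that it does. Asking the sponsor whether the sentence is current would be a reasonable courtesy query, but no result depends on the answer.
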